#### Implanted EEG electrodes:

Subdural strip electrodes consist of a series of metallic electrodes mounted in thin plastic in such a way that it can lie smoothly on the surface of the cortex. They provide high amplitude ECoG signals, and are widely used for monitoring, seizure mapping and stimulation for functional mapping. Subdural strip electrode implantation, mostly used for identifying the epileptogenic focus in epilepsy patients, is a relatively safe procedure (Wyler et al., 1984). The application of strip electrodes is not restricted to epilepsy patients. In movement disorder patients, positive effects of chronic motor cortex stimulation via epidurally implanted electrodes have been first reported by Canavero and Paolotti (2000) and Canavero et al., 2002 and Canavero et al., 2003, by implanting the strip electrodes extradurally over M1 via a small craniotomy. The results of recent studies on Parkinson's patient during deep brain stimulation surgery demonstrate that subdural strip electrode implantation over human motor cortex is safe (de Hemptinne et al., 2013, de Hemptinne et al., 2015). These recordings provide a unique opportunity to investigate the mechanisms of action of deep brain stimulation in

Date: February 19, 2023

Principal Investigator: [name].

Application Number: NA\_00079932

movement disorders in general and Parkinson's Disease specifically (Crowell et al., 2012, de Hemptinne et al., 2013, de Hemptinne et al., 2015).

In traditional subdural electrode strip placement procedures, the associated risk of infection is greatest when there are more than 100 electrode contacts implanted, an excess of 10 exiting electrode cables, or if the electrodes remain for 14 days or more (Fountas , 2011). Infection is not a major risk in the procedure as proposed because the electrode is left in place for a much shorter time span (4 hours) than typical strip placement procedures (7-14 days). Additionally, the cables pertaining to the electrodes remain within the sterile field for the duration of the procedure, further decreasing the risk of infection. Another risk of electrode placement is hemorrhage. Significant intracerebral hemorrhage has been reported, with an incidence of 2.5% from 1,582 patients assessed with depth electrodes from a literature review (Pilcher et al., 1993, 2004), and 1% or less incidence in a more recent study (Blume, 1997).

Fountas (Fountas, 2011) found hemorrhages to be limited and scattered. Postimplantation edema has been reported, with occurrences varying between 0.5% and 14% (Fountas , 2011; Van Gompel et al., 2008; Hamer, et al., 2002). Although the exact pathophysiologic mechanism of edema associated with subdural electrode placement remains unclear, it is hypothesized that edema development is a result of compression of large cortical veins by large subdural grids. Edema may be reduced by systematic administration of steroids (Fountas, 2011), or the use of smaller strip electrode arrays. Postimplantation edema poses the greatest risk in young patients, previously damaged cortical areas, or involving electrode grids with large surface areas and thus is unlikely to affect our proposed subjects.

#### Direct Pulsed Cortical Stimulation:

Intraoperative application of electrical current to the cortex in patients with tumors or epilepsy has become a standard technique during brain surgery for inferring the function of brain areas. While the patient performs motor, language or cognitive tasks under controlled conditions, the cortical surface is stimulated with a strip or grid electrode to provoke reproducible, transient changes in behavior (Borchers et al., 2012). For example, the representation of language functions was mapped to the human left hemisphere (Ojemann et al., 1989, 1991; Duffau et al., 2003,2005; Sanai et al., 2008) whereas spatial processing of visual objects (Thiebaut De Schotten, M. et al.2005) and spatial orienting and exploration (Gharabaghi et al., 2006; Kleinman et al., 2007) were mapped to the human right hemisphere.

#### Studies of Cortical Stimulation in Parkinson's Disease

Cortical stimulation for the treatment of Parkinson's disease has been investigated recently (Lefaucheur, 2009). Here, cortical stimulation is mostly performed after chronic implantation of strip electrodes over the motor cortex. Following closure of the craniotomy, the electrode cable(s) are connected to a trial stimulator. Based on over 3–14 days of test stimulation, the best stimulation parameters and electrodes are decided in terms of improvement in Parkinson's symptoms. Among the total number of 37 Parkinson's disease patients that enrolled in a motor cortex stimulation study, the occurrence of epileptic seizures has been reported during test stimulation in a minority of patients N=1, Arle et al., 2008).

Date: February 19, 2023

Principal Investigator: [name].

Application Number: NA\_00079932

In this group of studies, most neurosurgeons attempted intraoperative test stimulation by using subdural grid electrodes. Test bipolar stimulation (210-1000  $\mu$ s –generally 400-500- $\mu$ s, 1-5 Hz up to 100Hz, with intensities up to 50 mA, anodally, and also cathodally) was applied by means of the contacts situated over the primary motor or sensory cortex. There were no other complications caused by the device or the implant procedure, and all patients tolerated the implantation procedure well. (De Rose et al., 2012; Canavero, 2015; Tani, and Saitoh, 2016). In contrast to these tonic stimulation studies, our proposed phase-dependent stimulation techniques represent a much narrower (reduced number of pulses) and much more transient (active only during specific bandpass power changes) (Chen et al., 2011, 2013) form of cortical pulsed stimulation, and we feel the chance of seizure production will be reduced for these reasons. The application of cortical stimulation is performed solely for research reasons as outlined here, to assess changes in subthalamic nucleus activity (Kim et al., 2008; Magill et al., 2001), and to assess possible clinical benefits for phase-dependent stimulation modalities. Since there is a risk of seizure with cortical stimulation, an IV antiepileptic (usually levetiracetam) ( Zachenhofer et al., 2011; Bahr et al., 2012; Kirmani et al., 2014; Jin et al., 2012) will be administered at the start of the surgical procedure. This is performed routinely for DBS lead placement procedures at Johns Hopkins due to the already present risk of seizures with the surgery.

### Studies of Cortical Stimulation in Patients with Epilepsy

Rates of stimulation induced seizures have been measured in patient groups with and without symptomatic epilepsy concomitant with a brain tumor. Szelényi et al. used stimulation currents up to 40 mA, and found that 1/63 (1.6%) patients in the symptomatic epilepsy group suffered a stimulation induced seizure (Szelényi et al., 2007). In the nonsymptomatic group, similarly, 1/66 (1.5%) suffered a stimulation induced seizure. The range of reported seizure induction for intraoperative stimulation is from 1.2% (for a train of five stimulation technique) up to 9.5% for continuous 60 Hz stimulation (Szelényi et al., 2007). Zangaladze et al. also studied a series of invasively monitored patients undergoing cortical stimulation for mapping and used stimulation currents up to 17.5 mA at several stimulation frequencies (5-50Hz) (Zangaladze et al., 2008). These authors found that the production of neighboring electrode after discharges (which herald the onset of a seizure) are greatly reduced with lower stimulation frequencies while the actual cortical mapping is just as sensitive (Zangaladze et al., 2008). To further clarify, these stimulation induced seizure estimates occur in patients with known seizures or epilepsy. Subjects considered for this study do not have seizure disorders, and will be excluded from stimulation studies if there is a history of any seizure episode. Of note, a similar stimulation protocol involving phase dependent stimulation in epilepsy patients has been approved by the Johns Hopkins IRB under Protocol # IRB00040308.

The use of stimulation in the protocol described in this grant is much less intense than stimulation paradigms typically used for mapping. Phase-dependent stimulation techniques use subthreshold stimulation current levels timed to transiently measured periods of rhythmic activity generally lasting for only a few seconds. Monitoring for after discharges in neighboring electrodes will be used as a stopping point for further stimulation. After discharge monitoring is used routinely in the epilepsy community as a sign to abort cortical stimulation at a particular electrode (Lesser et al., 1999; Motamedi et al., 2002 ; Ojemann et al., 1989, 1991). Stimulation testing will be aborted and no further testing will be performed on subjects exhibiting after discharges.

Date: February 19, 2023

Principal Investigator: [name].

Application Number: NA\_00079932

Because of the additional subdural strip cabling present on the sterile field, there is a theoretical increased risk of postoperative infection. The strip itself is sterilized as well as the associated cabling preoperatively. Subjects undergo postoperative staple removal and wound check appointments with the surgeon involved in these procedures, and oral antibiotics are started at the sign of any stitch abscess or localized skin infection. Infections can necessitate the explantation of the DBS system. Psychosocial risks should be no higher than that already associated with awake intraoperative testing using microelectrode recording. There are no additional radiation risks associated with this protocol. The patients undergo a preoperative head CT examination for targeting and trajectory planning (when fused with the preoperative high resolution MRI), intraoperative imaging including fluoroscopy and O-arm modalities for lead localization, and an immediate postoperative head CT and later brain MRI examination after the surgery to assess lead placement.

### Auditory Stimulation and Speech Recording

Auditory stimulation and speech production recordings are completely noninvasive and there are minimal to no risks associated with this kind of testing. Auditory stimulation is kept at a normal conversation level (<60 dB) to protect the ears (Way et al., 2013; Liu et al., 2000).

#### **a. Steps taken to minimize the risks.**

- i) Risks related to computer-controlled sensory tests (laser and contact thermode) are controlled by software limits, and by limitation of the power delivered by any stimulator. With these tests (number 1 above section 'Medical risks listing ...') and with the ice water test, the patient will have the ability to remove his hand from the water at any time.
- ii) Risks related to the ischemia test (number 2 above) will be minimized by having the investigator at the patients side throughout the test, prepared to deflate the cuff at any time.
- iii) The risks of motor testing (number 3 above) are controlled by limits of the torque motor excursion and by the patients' ability to release the manipulandum at any time; any member of the research team will be able to disable the stimulator if they observe unexpected movements of the motor. All subjects will have the option to withdraw from any protocol without penalty.
- iv) For the tDCS system, we will use either Conventional rectangular sponge pad: we will use a pair of saline-soaked surface sponge electrodes (anode:  $7 \times 5 \text{ cm}^2$ ; cathode:  $7 \times 5 \text{ cm}^2$ ). The anode electrode will be positioned over the motor cortex representational area of the hand region on an affected side, and the return electrode will be placed above the contralateral motor cortex area or  $4 \times 1$  Ag/AgCl ring electrodes: with plastic holders filled with EEG conducting gel. This will reduce the total applied current and increase the stability of stimulation. The  $4 \times 1$  ring configuration will increase the flexibility of electrode placement with respect to the burr holes and also will allow focal stimulation of the motor cortex ( Datta et al., 2010). This allows for a very low intensity current stimulation level. Even in the worst case, the current density generated by transcranial direct current stimulation on healthy head with a two electrode montage ( two  $5 \times 5 \text{ cm}$

Date: February 19, 2023

Principal Investigator: [name].

Application Number: NA\_00079932

electrode pads) using 2 mA on the bilateral primary motor cortex ( C3 anodal an C4 cathodal), is about  $0.95 \text{ A/m}^2$  which is far below the tissue damage threshold . Brain tissue damage generally occurs at a current density of  $142.9 \text{ A/m}^2$  or greater (Liebetanz et al., 2009).

- v) With regard to the potential for patient fatigue or frustration while performing the speech production task, patients will be closely monitored for signs of stress, and patients will be asked if they would like to take a break or to stop participation in the task altogether.
- vi) The risks for direct pulsed cortical stimulation are similar to the risks already present during awake deep brain stimulation lead placement procedures, with the exception of the addition of the phase-dependent selective pulse stimulation using the cortical strip. In that regard, we will exclude patients with underlying seizure disorders, history of epilepsy and under treatment with medications that can provoke seizures. Both the techniques of ECoG recording and stimulation while monitoring for after discharges represent established techniques for recording ictal and interictal periods and for brain mapping in the invasively monitored epilepsy population. Monitoring for after discharges will be performed during this transient application of stimulation pulses. Stimulation currents will be kept  $\leq 6 \text{ mA}$ . Keppra (2,000 mg for the typical range of patient weights) will be administered in IV form prior to skin incision. All testing will be aborted if afterdischarges are observed at any time.

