- 6) **Muscle Contraction (Ischemia) Test:** The blood supply to the participant's arm appropriate to the side of the procedure or the side of psychophysical testing will be cut off by placing a standard blood pressure cuff on the participant's arm and inflating the cuff to 220 mm/Hg. Then, the participant will be asked to grip a handle repeatedly while the cuff is inflated. Finally, the participant will be asked to relax his/her hand while the cuff remains inflated for another one to two minutes.
- 7) **Electrical stimulation of the Skin:** an FDA approved constant current stimulator (DS7A, Digitimer, Hertfordshire, UK) or a constant current stimulator (S12, Grass, Warwick, RI , U.S.A.) will be applied to the hand to produce a non-painful tingling sensation. The electric stimulus will be delivered through a pair of Ag/AgCl electrodes filled with isotonic paste (9-mm diameter, Docxs Biomedical Products,

Date: February 19, 2023

Principal Investigator: [name].

Application Number: NA\_00079932

Ukiah, CA) placed on the wrist. The subject will be free to remove the electrodes from her/his hands at any time.

8) **tDCS Stimulation:** The tDCS portion of the experiment will begin with DC current (maximum of 2 mA) stimulation delivered through surface electrodes (TransQE from IOMED®, surface area: 25 cm^2) using a Phoresor® II Auto (Model No. PM850, IOMED®, Salt Lake City, Utah 84120, USA). In some experiments, one electrode will be positioned above the primary motor cortex of an affected side, the other electrode will be placed over the forehead. In other experiments, one will be positioned over the primary motor cortex of an affected side and the other one above the contralateral motor cortex. Anodal or cathodal tDCS will be delivered for 20 min. The current will be increased in a ramp-like fashion to reduce the appearance of transient phosphenes usually present with rapid on-off applications. Previous studies have demonstrated that these parameters of tDCS modulate motor cortical function for up to 90 minutes following the end of stimulation and in a study in stroke patients this stimulation elicited motor performance improvements that outlasted the stimulation period.

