For sham stimulation the electrodes will be placed in the same way as for real tDCS in the absence of real stimulation, this means stimulation will be increased to a current strength near the perception threshold and will be decreased afterwards and set to 0 mA output for a period of 20 min. With this procedure participants are usually unable to differentiate between tDCS and sham stimulation.

After prepping and draping the subject's scalp for the surgical procedure, the tDCS electrode arrays will be positioned approximately over the hand region of the motor cortex following the guidelines of (Edwards et al., 2013; Kou et al., 2012; Villamar MF et al., 2013). We employ surface electrodes (TransQE from IOMED®, surface area: 25 cm^2) connected to a conventional tDCS device using a Phoresor® II Auto (Model No. PM850, IOMED®, Salt Lake City, Utah 84120, USA) to deliver DC to the scalp via electrodes. The central active electrode is placed above the representational area of the ADM muscles (approximately over C3 or C4 based on the International 10/20 EEG System corresponding to the laterality of Parkinson symptoms) and the reference electrode is located in contralateral motor cortex. The microelectrode will be positioned in the target of interest (subthalamic nucleus or globus pallidus interna), and recordings of multiunit and field potential activity as a baseline will take place for 5 minutes. Application of tDCS will then be performed at a set current of 2 mA for 10 minutes. Recordings of multiunit and field potential activity will take place during the application of tDCS and for a period of 5 minutes after the cessation of the tDCS.

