### **Transcranial Direct Current Stimulation (tDCS) Device**

Date: February 19, 2023

Principal Investigator: [name].

Application Number: NA\_00079932

We employ surface electrodes (TransQE from IOMED®, surface area: 25 cm^2) connected to a conventional tDCS device Phoresor® II Auto (Model No. PM850, IOMED®, Salt Lake City, Utah 84120, USA) to deliver DC current to the scalp via surface electrodes.

tDCS will be administered with a current strength of 2 mA for maximum of 10 min by a constant current stimulator. Based on subject restrictions two types of electrode configuration will be applied:

1. Conventional rectangular sponge pad: we will use a pair of saline-soaked surface sponge electrodes (anode: 7 × 5 cm^2; cathode: 7 × 5 cm^2). The anode electrode will be positioned over the motor cortex representational area of the hand region on an affected side, and the return electrode will be placed above the contralateral motor cortex area.

2. 4 × 1 ring: The central active electrode will be placed above the representational area of the unaffected side hand (coinciding with the center of the anodal pad used for regular-pad stimulation) and surrounded by four return electrodes (each at a ring center to ring center distance of 3.5 cm from the active electrode) which will be connected to a four-to-one wire adaptor for the DC stimulator. Altogether five sintered Ag/AgCl ring electrodes (outer radius: 12 mm, inner radius: 6 mm) will be stabilized with plastic holders filled with EEG conducting gel (H + H Medical Devices, Germany and with gel-skin contact area ~25 ± 2.5 mm^2). Since the sensation to tDCS could differ with electrode and gel type (Minhas P, et al. 2010), here we will apply the suggested Ag/AgCl sintered ring electrodes (Minhas P, et al. 2010), and the conducting gel for less skin sensation as reported by the subjects.

Numerous methods utilize external landmarks to locate the motor strip (pre central gyrus). The motor strip typically lies anywhere from 4 to 5.4 cm behind the coronal suture. Based on the International 10/20 EEG system the C3 and C4 locations correspond to the left and right motor cortex (Edwards et al., 2013; Kido et al., 1980; Sarmento et al., 2008; Ebeling et al., 1987).

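### The two-orders-of-magnitude charge margin stated for intraoperative tDCS holds for the pads at 2 mA for 10 min, but not for the 4 × 1 ring planned at the same current

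*Combined protocol and SAP*

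**What the plan says.** **Dose.** Section 6, under the tDCS device, states: "tDCS will be administered with a current strength of 2 mA for maximum of 10 min by a constant current stimulator". The next sentence reads "Based on subject restrictions two types of electrode configuration will be applied", and two configurations follow: a pair of 7 × 5 cm sponge pads, and a 4 × 1 ring with one central active electrode and four return electrodes. The same subsection also names a 25 cm² surface electrode. The intraoperative sequence in section 4 (test stimulus 8) agrees on dose: "Application of tDCS will then be performed at a set current of 2 mA for 10 minutes". The general description earlier in that item says "Anodal or cathodal tDCS will be delivered for 20 min".

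**Ring size.** One sentence in section 6 gives the ring electrodes as "outer radius: 12 mm, inner radius: 6 mm" and also gives their contact area: "and with gel-skin contact area ~25 ± 2.5 mm" (square millimetres).

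**Safety argument.** The tDCS risk text in section 8 cites a rat study with an epicranial electrode. Lesions occurred at 142.9 A/m² for more than 10 min, and the fitted charge density for zero lesion size was 52,400 C/m². The protocol then says the upper limit for its intraoperative use is two orders of magnitude below that charge density. Item iv of the risk-minimising steps describes the pads and the ring and adds "This will reduce the total applied current and increase the stability of stimulation". It continues with "Even in the worst case, the current density generated by transcranial direct current stimulation on healthy head with a two electrode montage", meaning two 5 × 5 cm pads at 2 mA, and gives about 0.95 A/m².

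**The concern.** A constant-current device delivers its set current whichever electrode is attached. Moving from a pad of 25 or 35 cm² to a ring electrode of a few square centimetres or less therefore raises both current density and charge density at the electrode. The protocol gives one current for both configurations, yet its charge margin and its worst-case density appear to have been worked out for pads only. The current reduction listed as a safeguard has no number behind it.

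What is at stake is the quantitative safety argument for intraoperative tDCS. Item iv prefers the ring for its flexibility around burr holes, so its use in these patients is foreseeable. Anyone judging the protocol would take the margin of about 100-fold and the 0.95 A/m² as applying to both configurations.

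**Working it through.** **Inputs.** Current I = 2 mA = 0.002 A (sections 4 and 6). Duration t = 10 min = 600 s (section 6, and the intraoperative sequence in section 4). Thresholds 52,400 C/m² and 142.9 A/m² (section 8). Pad areas 35 cm² (7 × 5 cm) and 25 cm². The ring's central electrode is taken to carry the full 2 mA, with three readings of its area:

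- full disc of 12 mm radius: π × 12² = 452 mm²
- annulus with 12 and 6 mm radii: π × (12² − 6²) = 339 mm²
- printed contact area: 25 mm², tolerance 22.5 to 27.5 mm²

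The annulus and the printed area differ by 339 / 25 = about 14-fold.

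**Formulas.** Current density J = I / A. Charge density Q = J × t. Charge margin = 52,400 / Q. Current margin = 142.9 / J.

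**Reproducing the plan's figure.** For the 35 cm² pad, J = 0.002 / 0.0035 = 0.57 A/m², Q = 343 C/m², margin 153. For the 25 cm² pad, J = 0.80 A/m², Q = 480 C/m², margin 109. The stated two orders of magnitude is therefore right for pads at 10 min.

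**The same calculation for the ring, 2 mA for 10 min:**

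| Electrode | J (A/m²) | Q (C/m²) | Charge margin | Current margin |
|---|---|---|---|---|
| Pad, 35 cm² | 0.57 | 343 | 153 | 250 |
| Pad, 25 cm² | 0.80 | 480 | 109 | 179 |
| Ring, disc 452 mm² | 4.42 | 2,653 | 19.8 | 32 |
| Ring, annulus 339 mm² | 5.89 | 3,537 | 14.8 | 24 |
| Ring, printed 27.5 mm² | 72.7 | 43,636 | 1.20 | 1.96 |
| Ring, printed 25 mm² | 80 | 48,000 | 1.09 | 1.79 |
| Ring, printed 22.5 mm² | 88.9 | 53,333 | 0.98 | 1.61 |

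The ring misses 100-fold on every reading. A 100-fold margin at this dose needs 0.002 × 600 / 524 = 0.00229 m², or 22.9 cm².

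**The 0.95 A/m² figure.** For its stated inputs, I / A = 0.002 / 0.0025 = 0.80 A/m². Obtaining 0.95 at 2 mA needs 0.002 / 0.95 = 0.0021 m², about 21 cm². So 0.95 is not the simple electrode density of a 5 × 5 cm pad. It may be a modelled value, or it may be the 0.095 mA/cm² quoted from another study earlier in section 8, which is numerically the same. The protocol does not say.

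**At 20 min.** Charge margins halve: pads 76 and 55; ring 9.9 (disc), 7.4 (annulus) and 0.55 (25 mm²).

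**The case against.** **Electrode densities are not brain densities.** This stands. The thresholds come from a rat epicranial electrode, and item iv speaks of damage to brain tissue. A reader might infer from the 1.1-fold figure that the ring would injure the cortex. The documents do not support that. Every ring reading is below 142.9 A/m², and section 8 reports that brains stimulated below either threshold looked like unstimulated controls. Its linear relation between lesion size and charge density was also fitted only from 142.9 to 285.7 A/m², above every ring value here. For the same reason, 0.95 A/m² is not shown to be wrong for brain tissue. It is only not shown to cover the ring, and item iv does print its limits (intact head, two pads).

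**The near-threshold figures rest on an area that may be a misprint.** This also stands, and it is why a range is given. It does not rescue the claim: 15- to 20-fold, on the printed radii, is about one order of magnitude.

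**The 20 min figure.** A reader might conclude that the claim also fails for the pads. But it is confined to intraoperative use, which sections 4 and 6 set at 10 min, and 55- to 76-fold could loosely pass as two orders (log10 of 1.74 to 1.88). The conflict in duration needs tidying but carries no weight in this finding.

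**The reduced-current sentence is ambiguous.** Its subject could be the ring, the gel holders or both. On any reading, no lower current is specified.

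**Who relied on the margin.** A reader might suppose that patients were told of a 100-fold margin. The consent pages are not available, so nothing visible shows that.

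**Conclusion.** The point holds for the ring. At 2 mA for 10 min the stated charge margin is correct for the pads (109- to 153-fold) and false for the ring's central electrode: about 15- to 20-fold on the printed radii, and about 1.1-fold (0.98 to 1.2) on the printed contact area. The protocol cannot settle which applies, because its two descriptions of the ring disagree. The contact area matters for the human comparison too. The highest human density that section 8 cites is 25.46 A/m² for 20 min. The ring is 0.17 to 0.23 times that on the printed radii and 80 / 25.46 = 3.1 times on the printed area.

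The current reduction is unsupported by any stated dose, and 0.95 A/m² is a pad figure of unclear origin.

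This rests on two assumptions: the central electrode carries the full set current, and the density is uniform over its contact area. It shows an error in a stated safety margin for a planned configuration, not a hazard. The effect of burr holes is not part of it.

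**What to change.** - **Section 6:** measure and correct the ring's contact area before the ring is used at 2 mA.
- **Section 8, tDCS risks:** limit the two-orders claim to the pads at 10 min. Give current density and charge density for the ring separately, against both 142.9 A/m² and 52,400 C/m².
- **Section 8, item iv:** delete the reduced-current sentence, or specify the ring current here and in sections 4 and 6. Drop the worst-case wording. Label 0.95 A/m² as a pad-only, intact-head figure, check its derivation, and say whether it is a modelled or an electrode value.
- **Section 4, test stimulus 8:** make the 20 min consistent with the 10 min maximum for intraoperative use.

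Lowering the ring current to reach 100-fold is not required, since that margin is a descriptive remark and not a safety standard. If the sponsor does choose a lower ring current, pad and ring recordings would be at different doses and could not simply be pooled.

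The cost is one device measurement, a small table and amendment wording. The downside is a less favourable stated margin.
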